9.4 Withdrawal of individual subjects

Subjects can leave the study at any time for any reason if they wish to do so without any consequences. The investigator and sponsor can decide to withdraw a subject from the study for urgent medical reasons.

9.5 Replacement of individual subjects after withdrawal

For this study subjects will not be replaced after withdrawal.

9.6 Follow-up of subjects withdrawn from treatment

All patients taking study medication will be followed up for a maximum of 2 years and 3 months, when tapering of study medication is complete. When a patient prematurely discontinues study medication a full end of study visit (V9) is performed. This visit includes radiographic assessment (X-ray and DEXA) if study medication is stopped at or after 9 months from study start and if local standards permits.

Where this is not possible (because the stop of study medication lies in the past), the first visit after the event must be executed as a V9 visit.

For completeness: regulations stipulate that all adverse events (serious or nonserious) MUST be followed until resolved or stable, this also applies to situations where study medication is prematurely stopped. For all adverse events the last possible follow up will be at V10.

In addition, all patients stopping prematurely are invited to attend a follow up visit (V10) at or around 2 years after the inclusion date. Data collected at this visit is the same as those collected for a normal V10 ('follow up/taper visit').

For patients who stop prematurely, AE evaluation will be limited to SAE and events of special interest. At visit 10, completeness of follow up for events occurring in the first 3 months after stop of study medication will also be checked.

Completion of the data for V10 is required to receive the full fee for a patient.

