7. INTERVENTION/TREATMENT OF SUBJECTS

7.1 Investigational product

In this two-armed clinical trial, patients will be randomized to either the experimental arm or the control arm. The experimental arm will receive prednisolone 5 mg/day added to existing antirheumatic treatment. The control arm will receive matching placebo added to existing antirheumatic treatment. Both treatments will be given for the duration of two years.

Subsequently, study drug is slowly tapered in linear fashion to zero in 3 months by inserting increasing numbers of non-treatment days. For this purpose and to prevent unblinding, 3 months of extra study treatment will be made available. Patients experiencing a flare at that time can restart open label prednisolone at the discretion of the treating rheumatologist.

Co-medication

As part of standard of care all patients will receive Calcium 500 mg/Vitamin D3 800 IU. The supplement is beneficial in all RA patients, given the almost universally low levels of vitamin D and low intake of calcium in the diet of the target population.

Adherence

To measure adherence, an adherence medication packaging solution that combines Objective therapy Compliance Monitoring technology (OtCM) and special software is delivered. All patients will have an adherence monitoring device loaded into the cap of the drug bottle. Adherence data will be registered in the study database for all patients, and analysed at the end of the study. Furthermore, the use of RA-friendly pill bottles will avoid the difficulties many RA patients experience with blister packs (small size combined with the force required to push pills out).

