9.1.1 Main study outcomes

a) GC benefit/harm balance

Benefit

Primary outcome measure

- Signs and symptoms: the time-averaged mean value of the DAS28;

Secondary outcome measures

- Damage progression: 2-year change in total Sharp/van der Heijde damage score of hands and forefeet radiographs.
- WHO-ILAR core set of RA outcome measures, including pain, patient and physician global assessment, physical disability, joint counts (swollen joints and tender joints), acute phase reactants (C-reactive protein (CRP) and erythrocyte sedimentation rate (ESR)), and radiographs of hands and forefeet at 0 and 2 years
 - DAS28 is calculated is calculated from 4 of these
- Severity and duration of morning stiffness
- Fatigue
- SF36 - The Short Form 36-item Health Survey, a questionnaire about QoL
- RA Impact of Disease (RAID) tool – The RAID is a validated questionnaire assessing the seven most important domains of impact of RA on the patients
- Health Assessment Questionnaire (HAQ)
- cost questionnaire, including
 - Activity limitation (part of cost questionnaire)
 - Work disability (for those holding a paid job, part of cost questionnaire)
- Utility/Quality-adjusted life years (QALY): Euro-QoL in 5 dimensions (EQ-5D)

Harm

Primary outcome measure

The total number of patients experiencing at least one AE of Special Interest. An 'AE of Special Interest' is defined as either a SAE according to the GCP definition (described in chapter 10.2.2), or the occurrence of one the following AEs:

- any AE (except loss of efficacy, worsening of disease) that leads to the definite cessation of one of the antirheumatic drugs, including trial medication;

- a cardiovascular event (myocardial infarction, cerebrovascular event, peripheral arterial vascular event)
- newly occurring hypertension requiring drug treatment;
- newly occurring diabetes mellitus requiring drug treatment;
- symptomatic bone fracture requiring treatment;
- infection requiring antibiotic treatment;
- newly occurring cataract or glaucoma.

AEs can be reported spontaneously by patients, on prompting at clinic visits or by telephone interviews, and by the treating physician. The AEs specified above will be recorded with special care in a separate procedure. This procedure includes adjudication through the collection of evidence. This can be a declaration of the treating physician (in case of start of treatment), or a copy of a letter confirming the event, kept on file in the center.

Secondary outcome measures

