10.2 AEs, SAEs and SUSARs

10.2.1 Adverse events (AEs)

An AE is any untoward medical occurrence in a subject who has received study drug, or any untoward or unintended response to an experimental intervention which does not necessarily have a causal relationship with the treatment.

An undesirable medical condition can be symptoms (e.g. dizziness, flushing), signs (e.g. local progression of swelling or hematoma), disease or the abnormal results of an investigation (e.g. laboratory findings) temporarily associated with the use of a medicinal (investigational) product. Any worsening of pre-existing condition that is temporally associated with the use of the pharmaceutical product, is also an AE.

Situations where an untoward medical occurrence has not occurred (e.g., hospitalization for elective surgery, social and/or convenience admissions) do not represent AEs.

Subjects will be carefully monitored throughout the study for AEs. At each study visit, subjects will be asked to report any AE. All AEs are followed until they are resolved or stabilized, or until all attempts to determine resolution of the event are exhausted. The investigator will use his/her discretion in ordering additional tests as necessary to monitor the resolution of such events.

Each collected AE, regardless of the relationship to study drug, will be recorded in the AE eCRF. All entries should contain an event term, date of onset, date of resolution, severity, action taken, outcome, relationship to study drug, and a seriousness assessment. The investigator will document all AEs in the subject's source document. Reported (change in) symptoms in the "Patient symptom list" do not need to be reported in the eCRF as an AE.

Severity will be assessed by the investigator according to the following definitions:

- Mild: The event is of little concern to the subject and/or of no clinical significance. The event is not expected to have any effect on the subject's health or wellbeing.

- Moderate: The subject experienced discomfort enough to cause interference with usual activity, and/or the condition required specific treatment. The event is of some concern to the subject's health or wellbeing. The event may require medical intervention.

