### *Harm*

- Vital signs (heart rate and blood pressure), height, weight – at 0, 3, 6, 12, 18, 24, 27 months
- Bone mass assessed by Dual-energy X-ray Absorptiometry (DEXA) - at 0 and 24 months
- Vertebral Fracture Analysis (by DEXA OR lateral radiograph of thoracic and lumbar spine) - at 0 and 24 months
- Discontinuation of study drug with reason: this includes patients in whom treatment with prednisolone becomes clinically indicated or those with unacceptable side effects attributable to study medication
- Change of antirheumatic treatment, with reason
- Intensification of treatment for existing comorbidity, e.g. hypertension or diabetes
- Joint replacement surgery
- AEs, SAEs, other AESI at every study visit
- Concomitant medication at every study visit

Data collection is in agreement with industry standard (i.e. Meddra terminology etc.).

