Joint replacement surgery	35	Intent-to-treat population	Number of joint replacement surgeries	0, 3, 6, 9, 12, 15, 18, 21, 24 months	Treatment group	Continuous	n (%)

Table title	Number	Population	Endpoint	Time points or how to conglomerate	Covariates or subgroups	Type of variable	Summary statistics
AE, SAE, other AE of special interest summary	36A	Intent-to-treat population	Number of AEs, SAEs, other AEs of special interest	3, 24 months	Treatment group	Continuous	-Mean (SD) (median, min, max if data are non-normal distributed) -Top 3 of most common AE categories: 1. % (n) 2. % (n) 3. % (n)
	36B	Safety population	Number of AEs, SAEs, other AEs of special interest	3, 24 months	Treatment group	Continuous	-Mean (SD) (median, min, max if data are non-normal distributed) -Top 3 of most common AE categories: 1. % (n) 2. % (n) 3. % (n)
AEs, SAEs, other AEs of special interest	36C	Intent-to-treat population	Number of AE, SAE, other AE of special interest per organ system	3, 24 months	Treatment group	Categorical	-Category 1: n (%) -Category 2: (n%) -Category 3: n (%) Etc.

Table title	Number	Population	Endpoint	Time points or how to conglomerate	Covariates or subgroups	Type of variable	Summary statistics
36D	Safety population	Number of AE, SAE, other AE of special interest per organ system	3, 24 months	Treatment group	Categorical	-Category 1: n (%) -Category 2: (n%) -Category 3: n (%) Etc.	-Category 1: n (%) -Category 2: (n%) -Category 3: n (%) Etc.
37	Intent-to-treat population	Presence of SAE or other AE of special interest	24 months	Treatment group	Dichotomous	-Yes: n(%) -No: n(%)	

Figure 1 Patient disposition: consort flow chart

Figure 2 Premature discontinuation per treatment group: Kaplan-Meier survival curve

Figure 2 DAS28 score per treatment group over time

Figure 3 Number of SAEs and other AEs of special interest per treatment group : Kaplan-Meier survival curve

Figure 4 Probability density plot of x-rays at 0 and 24 months

Listing 1	Patient disposition
Listing 2	Patients excluded from the analysis populations
Listing 3	Protocol violations
Listing 4	Visit windows
Listing 5	Study completion including reason early withdrawal
Listing 6	Demographics and baseline characteristics
Listing 7	History of glaucoma and cataract
Listing 8	RA history
Listing 9.A	Medical history
Listing 9.B	Medical history with MedDRA Coding
Listing 10.A	Treatment not given according to protocol - interrupted
Listing 10.B	Treatment not given according to protocol – discontinued

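### SAP Tables 36A-D compare all-AE counts by arm at 24 months without time at risk, although AEs that are neither serious nor of special interest stop being evaluated when a patient stops study drug early

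*Protocol*

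**What the plan says.** **What is collected.** Protocol 10.2.1 sets a general rule: "Subjects will be carefully monitored throughout the study for AEs. At each study visit, subjects will be asked to report any AE". SAP 1.4.2 lists as a harm endpoint "AEs, SAEs, other AESI at every study visit". Protocol 9.6 makes an exception for early stoppers: "For patients who stop prematurely, AE evaluation will be limited to SAE and events of special interest".

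Three things continue after an early stop:
- SAEs are still collected.
- Events of special interest are still collected even when not serious, for example "infection requiring antibiotic treatment" (Protocol 9.1.1).
- AEs already known are still followed up: "For all adverse events the last possible follow up will be at V10".

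Protocol 9.6 also requires a full end-of-study visit (V9) at the stop, invites early stoppers to V10 at about two years, and adds: "At visit 10, completeness of follow up for events occurring in the first 3 months after stop of study medication will also be checked". It does not say which kinds of event that check covers.

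**What is tabulated.** In SAP section 7, Tables 36A (ITT) and 36B (safety) have the endpoint "Number of AEs, SAEs, other AEs of special interest", summarised as a mean with SD and the three commonest categories. Tables 36C and 36D give counts per organ system. All four are by treatment group with entries at 3 and 24 months. None specifies patient-time, an event rate, an on-treatment window or a note on when collection ended.

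**The concern.** A count per patient is comparable between arms only if the arms were observed for similar lengths of time. Here the protocol itself ends observation of ordinary AEs at a point that depends on the patient's course after randomisation. The discontinuation reasons that Protocol 9.1.1 names are that prednisolone becomes clinically indicated and that side effects are unacceptable. Both could plausibly occur at different rates in the two arms, and they could pull in opposite directions.

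At stake is how the general AE profile is read. AEs are a listed secondary harm endpoint, but SAP 4.9 and 4.13 give no analysis method for ordinary AEs, so Tables 36A-D are their only planned by-arm tabulation. Readers will compare the columns. In a trial meant to inform the balance of benefit and harm, a difference in counts caused by observation time could be taken for a difference in tolerability.

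**Working it through.** The plan states no figure on this point, so there is nothing to reproduce. The check is a comparison of texts followed by an illustration of size.

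**Step 1: which events the cut-off affects.**

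| Event type | Patient stays on drug | Patient stops early |
|---|---|---|
| SAE | collected | still collected |
| Other AESI, serious or not | collected | still collected |
| New ordinary AE | asked for at each visit | no longer evaluated |
| AE known at the stop | followed | followed, to V10 at the latest |

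Only the third row has unequal observation.

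**Step 2: whether another part of the plan compensates.**
- SAP 4.5 reports study duration by arm, but in the disposition table. It is not time on drug and is not linked to AE counts.
- SAP 4.2 assumes that harm assessment is complete because it is checked against source data. That cannot restore events the protocol no longer asks for.
- The planned survival curve of discontinuation by arm would show a difference in stopping, but does not adjust the counts for it.

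**Step 3: possible size.** All inputs here are assumptions, because the documents give no discontinuation rates. Let d be the share of an arm stopping early, m the mean month of stopping, and suppose ordinary AEs occur at the same constant rate in both arms. Mean months of collection per patient are

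T = 24 − d × (24 − m)

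and the expected count is proportional to T. With equal true rates, the ratio of mean counts, prednisolone to placebo, is T(pred) / T(plac).

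Example, 20% against 40% stopping with m = 6: T(pred) = 24 − 0.20 × 18 = 20.4; T(plac) = 24 − 0.40 × 18 = 16.8; ratio 20.4 / 16.8 = 1.21.

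| Stopping, pred / plac | m = 12 | m = 6 |
|---|---|---|
| 20% / 20% | 21.6 / 21.6 = 1.00 | 20.4 / 20.4 = 1.00 |
| 30% / 40% | 20.4 / 19.2 = 1.06 | 18.6 / 16.8 = 1.11 |
| 20% / 40% | 21.6 / 19.2 = 1.13 | 20.4 / 16.8 = 1.21 |
| 40% / 20% | 19.2 / 21.6 = 0.89 | 16.8 / 20.4 = 0.82 |

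Dividing each count by its own T returns 1.00 in every cell under these assumptions. The ratios apply to ordinary AEs. If the AE entry in the tables also includes SAEs and AESIs, which are collected throughout, its ratio would be nearer to 1.

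**The case against.** The strongest reply is that these tables are descriptive. They carry no test, and the interpretation rules in SAP 4.12 use only SAE or other AESI for harm. Readers will also have study duration and withdrawal reasons by arm, the discontinuation curve, a Kaplan-Meier figure for SAE and other AESI, and the 57-symptom list by arm. The 3-month entries are little affected. Capture may also not end exactly at the stop date, since a V9 visit with AE evaluation follows and the V10 check is loosely worded. If stopping is similar in the two arms, there is no distortion. All of this stands, and it limits the weight of the point. It does not supply the missing denominator.

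Four stronger readings are tempting, and the documents do not support them:
- **That all non-serious AEs cease to be collected.** Non-serious events of special interest continue, and under SAP 1.4.1 an AE that leads to definite cessation of trial medication is itself an AESI, unless it is loss of efficacy or worsening of disease.
- **That a planned time weighting was dropped.** The weighting by time in trial in Protocol 11.1 concerns the primary harm outcome and, separately, adherence. It was never planned for all-AE counts.
- **That the bias favours one arm.** The illustration runs in both directions.
- **That harm during the taper is left out in error.** Protocol 7.1 says "study drug is slowly tapered in linear fashion to zero in 3 months by inserting increasing numbers of non-treatment days", AEs are evaluated at 27 months, and no AE table has a 27-month entry. But the harm hypothesis in SAP 4.9.1 is defined over 24 months, taper AEs appear in Listings 30.A-C, and the SAE/AESI figure states no time limit. Patients who flare may also restart open-label prednisolone, so a by-arm comparison in months 24-27 would be selected and contaminated.

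**Conclusion.** The point holds for ordinary AEs in Tables 36A-D. Followed as written, the plan displays 24-month counts whose collection period depends on when each patient stopped study drug, with nothing in the tables to show or adjust for it. The comparison is distorted only if time to stopping differs between arms. Under equal true rates, a constant AE rate, 20-40% stopping per arm and a mean stop at month 6 or 12, the count ratio would range from about 0.82 to 1.21, and would be 1.00 with equal stopping. Which value applies cannot be known from the documents.

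A reader might infer that the trial's harm conclusion is compromised. It is not affected by this rule: SAEs and other AESIs are still collected after an early stop, and they alone form the co-primary harm outcome and Table 37. This is an inexpensive improvement to safety reporting, not a defect in the primary analysis.

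**What to change.** In SAP section 7:
1. In Tables 36A-D, report all-AE and organ-system counts for the on-treatment period, from first dose to stop of study drug and ending at month 24 for the 24-month entry. Give patient-years and events per 100 patient-years by arm, with a rate ratio and 95% CI.
2. State the collection cut-off for ordinary AEs in the table titles.
3. Keep full 24-month counts only for SAE and other AESI.
4. Say that onset and stop dates define these windows, because SAP 4.4.2 otherwise assigns data by visit number and sets calendar visit dates aside.

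Protocol 9.6 and 10.2.1 should also be reconciled, so that it is clear what is collected after an early stop and which events the V10 completeness check covers.

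The cost is a little programming. Onset dates are recorded for each AE under Protocol 10.2.1, and the planned discontinuation curve already needs stop dates, so no new data are required. The limits should be stated with the tables: simple rates assume a roughly constant hazard, and they do not remove bias if patients stop for reasons related to their AE risk. A by-arm summary of AEs in months 24-27, for patients who entered the taper, is an optional descriptive addition and not a correction.

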9.7 Premature termination of the study

Not applicable: prednisolone at doses exceeding 5 mg/d is currently widely used as chronic therapy in the target population, so unexpected safety findings that would necessitate premature termination are extremely unlikely. One of the main objectives of the study is to provide an accurate estimate of the safety this licensed therapy.

9.8 Procedure for unblinding of study medication

The treating physician or pharmacist can request unblinding of study medication for medical reasons. Please refer to the Gloria IMP manual for unblinding instructions via the ALEA e-CRF or via telephone.

Full documentation will subsequently be collected by the Clinical Research Associate in that country.

The patient can stay in the study, but the data collected will be handled separately in the analysis (see section 7.2).

10. SAFETY REPORTING

10.1 Disadvantageous event

In accordance to applicable legislation and guidelines, the investigator will inform the subjects and the reviewing accredited ethical committee if anything occurs, on the basis of which it appears that the disadvantages of participation may be significantly greater than was foreseen in the research proposal. The study will be suspended pending further review by the accredited ethical committee, except insofar as suspension would jeopardise the subjects' health. The investigator will take care that all subjects are kept informed.

10.2 AEs, SAEs and SUSARs

10.2.1 Adverse events (AEs)

An AE is any untoward medical occurrence in a subject who has received study drug, or any untoward or unintended response to an experimental intervention which does not necessarily have a causal relationship with the treatment.

An undesirable medical condition can be symptoms (e.g. dizziness, flushing), signs (e.g. local progression of swelling or hematoma), disease or the abnormal results of an investigation (e.g. laboratory findings) temporarily associated with the use of a medicinal (investigational) product. Any worsening of pre-existing condition that is temporally associated with the use of the pharmaceutical product, is also an AE.

Situations where an untoward medical occurrence has not occurred (e.g., hospitalization for elective surgery, social and/or convenience admissions) do not represent AEs.

Subjects will be carefully monitored throughout the study for AEs. At each study visit, subjects will be asked to report any AE. All AEs are followed until they are resolved or stabilized, or until all attempts to determine resolution of the event are exhausted. The investigator will use his/her discretion in ordering additional tests as necessary to monitor the resolution of such events.

Each collected AE, regardless of the relationship to study drug, will be recorded in the AE eCRF. All entries should contain an event term, date of onset, date of resolution, severity, action taken, outcome, relationship to study drug, and a seriousness assessment. The investigator will document all AEs in the subject's source document. Reported (change in) symptoms in the "Patient symptom list" do not need to be reported in the eCRF as an AE.

Severity will be assessed by the investigator according to the following definitions:

- Mild: The event is of little concern to the subject and/or of no clinical significance. The event is not expected to have any effect on the subject's health or wellbeing.

- Moderate: The subject experienced discomfort enough to cause interference with usual activity, and/or the condition required specific treatment. The event is of some concern to the subject's health or wellbeing. The event may require medical intervention.
- Severe: The subject is incapacitated and unable to work or participate in many or all usual activities. The event is of definite concern to the subject and/or poses substantial risk to the subject's health or wellbeing. The event is likely to require medical intervention and/or close follow-up.
- Life-threatening: The subject is at risk of death due to the AE as it occurred. This does not refer to an event that hypothetically might have caused death if it were more severe.
- Death: Death related to AE.

Action taken is categorized as "none", "study drug discontinued", "dose modified", "required concomitant medication", "required procedure", or "other".

Event outcome at resolution, or time last follow-up was recorded is categorized as: "event resolved"; "resolved with sequelae"; "ongoing"; "lost to follow-up"; or "death".

The investigator will determine the relationship of the event to the study drug according to the following criteria:

- Not related: The event does not follow a plausible chronological sequence relative to trial medication administration and can be clearly assigned to other factors, such as subject's clinical condition, therapeutic procedures or administration of concomitant medications.
- Possibly related: There is sufficient information to accept the possibility of a causal relationship, although the connection is uncertain or doubtful, i.e. causal relationship is not impossible and not unlikely. The event follows a plausible chronological sequence relative to trial medication administration and/or presents the usual response to the drug tested. The event might also be caused by other factors, such as the subject's clinical condition, therapeutic procedures or administration of concomitant medications.
- Probably related: There are good reasons and sufficient documentation to assume a causal relationship in the sense of plausible, conceivable, likely, but not necessarily highly probable. The event follows a plausible chronological sequence relative to trial medication administration and/or presents an unexpected response to the trial drug and cannot reasonably be explained by other factors, such as the subject's clinical condition, therapeutic procedures or administration of concomitant medications.
- Definitely Related: When the event cannot be attributed to the subject's underlying medical condition or other concomitant therapy and there is compelling temporal relationship between the onset of the event and the study investigational product administration that leads the PI to believe there is evidence of a reasonable causal relationship.

